### **1.5 Study Population**

200 women with early stage breast cancer (TIS, T1-2, N0) removed with breast conserving surgery achieving a negative pathologic margin may be enrolled.

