The MammoSite® RTS (Hologic) breast brachytherapy balloon device was designed to treat a similar volume around the lumpectomy cavity compared to interstitial brachytherapy but with a single skin entry point. The device received FDA clearance in May 2002, and provides a simpler, less user-dependent method of APBI. Since the US Food and Drug Administration (FDA) approved the original single-lumen MammoSite RTS (Hologic), the use of brachytherapy is believed to have increased dramatically. A study of Medicare billing claims among women treated with BCT estimated that the use of brachytherapy as a component of oncologic care increased in incidence from less than 1% of cases in 2001 to 10% of cases by 2006. The American Society of Breast Surgeons has enrolled and followed a cohort of 1,440 women treated with the single-lumen MammoSite catheter on a registry trial. This group has reported a 5-year actuarial IBTR rate of 3.8%. Of the patients in this study, 90.6% had good-to-excellent cosmesis, 13% developed symptomatic seromas, 9.5% developed an infection, and 2.3% developed fat necrosis, results comparable to those seen with MIB.

More recent multiple-lumen devices allow greater flexibility in treatment planning, enabling both better coverage of the target tissue at risk and decreased dose to the nearby structures such as rib and skin. The Contura™ MLB (SenoRx, Irvine, CA) brachytherapy balloon device is a second-generation single-entry applicator that adds 4 additional lumens, offset by 5 mm, to the central channel. Similarly, the SAVI applicator (Cianna Medical, Aliso Viejo, CA) also has multiple strut-adjusted lumens allowing greater dose optimization than single lumen devices.

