##### **5.1.2 Secondary Endpoints**

5.1.2.1 We expect that estimated 3-year local control rate (using Kaplan-Meier method) should be greater than 95% (corresponding to a 3-year local failure rate of 5% or lower). We will assess 3- year estimates of local control using the Kaplan-Meier method.

5.1.2.2 The percentage of patients with good/excellent cosmetic results at 2-years should exceed 80%.

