## **15. STATISTICAL CONSIDERATIONS**

### **15.1 Patient Accrual**

Following IRB approval at all participating accrual sites, an accrual rate of 5-10 patients per month is anticipated.

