## 15.3 Sample Size Justification

The treatment will be considered unsafe if a 2-year serious toxicity rate exceeding 10% cannot be excluded with the 95% interval. Serious toxicity in this study is defined as toxicity greater than grade 2 using CTCAE v4.0 criteria. To be scored as a serious toxicity counting toward the primary endpoint, the toxicity must have a “probable” or “definite” attribution to the study treatment. In a cohort of 200 patients, there should be 11 or fewer serious toxicities to exclude a rate of 10% using the upper limit of the 95% confidence interval.

The primary purpose of this trial is to ensure that the delivery of short-course accelerated partial breast irradiation (APBI) will result in a rate of serious toxicity that is similar to that reported for conventional fractionation schemes. Specifically, the treatment will be considered safe if we are confident that the 2-year serious toxicity rate doesn't exceed 0.10. Assuming that the probability of serious toxicities with the conventional procedure is 0.03, with a sample size of 200 patients, if we observe up to 11 serious toxicities, the upper 95% confidence limit will not exceed 0.10. The relative threshold toxicity rates for different sample sizes has been generated and is available for review from the PI.

A secondary endpoint is local control. We will follow patients until the last enrolled patient has a minimum follow-up of 2 years; thus the expected median follow-up of the study population will be 3-4 years. This will allow for a Kaplan-Meier estimate of local control at 3 years. We expect local control to be greater than 95%.

In addition to toxicity, cosmesis will be followed and evaluated as a secondary endpoint. Cosmesis will be evaluated by determining the number and percent of patients within each response category (Excellent, Good, Fair, Poor) at yearly intervals. Additionally, calculating the distribution of responses after collapsing into Excellent/Good versus Fair/Poor categories will be performed. Associations between dichotomous cosmetic outcomes (Excellent/Good versus Fair/Poor) and treatment related variables will be explored.

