## 15.6 Statistical Analysis

All time intervals will be calculated from the date of device removal. Fisher's exact test will be performed to correlate clinical-pathological covariates with toxicity and with cosmesis. The association of variables with LR failure times will be investigated by fitting a parametric model and examining the significance of the parameter estimates. Nonparametric estimates of the survival or recurrence-free distributions or recurrence (failure) distribution will be obtained by life table methods. Tests will be declared statistically significant if the calculated  $P$ -value was  $\leq 0.05$ . All tests appear as 2-sided  $P$ -values.

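### Section 15.6 tests covariates for LR failure with a parametric model on roughly 4 to 12 failures, with no small-sample method, no limit on terms and little power.

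*Combined protocol and SAP*

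**What the plan says.** Section 15.6 investigates the association of variables with LR failure times "by fitting a parametric model and examining the significance of the parameter estimates". The same section sets two-sided P ≤ 0.05 as the threshold for all tests. It gives no distribution, covariate list, limit on terms, estimation method, minimum number of failures or rule for non-convergence. Sections 15.7 and 15.9 only refer back to 15.3, which does not discuss this model. LR is not defined.

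The expected number of failures has to be inferred:

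- Section 1.5 sets enrolment at "200 women with early stage breast cancer".
- Section 5.1.2 expects local control above 95%, "corresponding to a 3-year local failure rate of 5% or lower". Section 15.3 repeats it: "We expect local control to be greater than 95" per cent.
- Section 15.3 sets the follow-up: "We will follow patients until the last enrolled patient has a minimum follow-up of 2 years". Section 15.1 says that "an accrual rate of 5-10 patients per month is anticipated".
- Section 2.3 supplies a background rate from the balloon registry: "This group has reported a 5-year actuarial IBTR rate of 3.8" per cent.

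Section 15.4 fixes the only covariate frequency in the plan, a minimum of 50 multicatheter cases.

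**The concern.** A failure-time model judged by the significance of its coefficients needs failures at every level of every covariate, and enough of them for the standard errors to mean something. This trial expects very few.

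Two things can go wrong. First, if all failures fall in one level of a binary covariate, or a level of a multi-level factor has none, the maximum-likelihood estimate is infinite. Its standard error grows faster than the coefficient, so the Wald P-value tends to 1. The check that Section 15.6 describes could then set aside the very covariate that separates failures from non-failures. Second, where estimates are finite, only very large ones can reach P ≤ 0.05. A non-significant covariate then carries almost no information, and a significant one will usually overstate its effect.

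What is at stake is how any reported predictor of recurrence, or the absence of one, can be read. Section 15.6 uses Fisher's exact test, a small-sample method, for toxicity and cosmesis, but names nothing comparable for local failure.

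**Working it through.** **Plan's own figures.** The plan states no failure count for this model. Its one stated event threshold is the toxicity rule in 15.3, 11 of 200. That rule reproduces (Clopper-Pearson upper limit 0.0963; 12 of 200 gives 0.1025) and has no bearing on this model.

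**Expected local failures.** By year 3 at the ceiling: 200 × 0.05 = 10.

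Over full follow-up, assume a constant hazard λ = −ln(1 − F)/T, where F is the failure rate at T years, and follow-up uniform from 2 to b years. The expected count is

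200 × [1 − (e^(−2λ) − e^(−bλ)) / (λ(b − 2))].

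Accrual of 200 at 5–10 per month takes 20–40 months; Section 3.2 allows 3 years. So b = 3.67, 5 or 5.33.

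| Rate | λ per year | 20 months | 36 months | 40 months |
|---|---|---|---|---|
| 5% at 3 years (plan's ceiling) | 0.0171 | 9.5 | 11.6 | 12.1 |
| 3.8% at 5 years (registry) | 0.0077 | 4.3 | 5.3 | 5.6 |

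This is the range of roughly 4 to 12. The 1% at 60 months that Section 2.3 gives for the interstitial series would mean only 1.1–1.5. The count would be higher if LR includes regional failures.

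**Chance of no finite estimate, one binary covariate.** With prevalence p, no true effect and exactly E failures, the chance is p^E + (1 − p)^E. With a Poisson count of mean m it is e^(−mp) + e^(−m(1−p)) − e^(−m). For multicatheter, p = 50/200 = 0.25:

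- m = 10: 0.0821 + 0.0006 − 0.00005 = 0.083, about 8%. With exactly 10 failures it is 5.6%.
- m = 5: 0.2865 + 0.0235 − 0.0067 = 0.303, about 30%. With exactly 5 failures it is 24%.

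**Any of five binary covariates.** The documents give no other prevalences, so two assumed sets show the range. For independent covariates, average 1 − ∏[1 − (pᵢ^E + (1 − pᵢ)^E)] over the Poisson count.

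| Assumed prevalences | Any of five, 10 expected | Mean number of five, 10 expected | Any of five, 5 expected |
|---|---|---|---|
| Evenly spaced, 15–30% | 44% | 0.61 | 81% |
| 50, 40, 40, 30, 25% | 16% | 0.19 | 55% |

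**Multi-level factors.** Lesion location on CRF #1 (Appendix 6) has five levels. If they were equally frequent, at least one would have no failures in 48% of trials with 10 failures and 96% with 5.

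**Precision and power at a 25:75 split.** SE of the log hazard ratio ≈ √[1/(E × 0.25 × 0.75)].

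- E = 10: SE = √(1/1.875) = 0.73. The estimate must exceed e^(1.96 × 0.73) ≈ 4.2.
- E = 5: SE = √(1/0.9375) = 1.03. The estimate must exceed about 7.6.
- Power for a true hazard ratio of 2 with 10 failures: Φ(0.693/0.730 − 1.96) = Φ(−1.01) = 16%.
- Failures needed for 80% power: (1.96 + 0.84)² / (0.693² × 0.1875) ≈ 88.

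**The case against.** Several points on the other side stand.

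- **Penalty.** A reader might infer that an unpenalised model is planned. The documents do not say so; Section 15.6 is silent on estimation. The supportable statement is that no penalty or other small-sample method is specified.
- **Extent.** A reader might infer that many covariate effects will have no finite estimate, or that the analysis will usually break down. The figures do not support that. At 10 expected failures the mean number of non-finite effects is 0.61 of five even with the less balanced prevalences, so most effects are estimable. With exactly 10 failures a single factor at 50% prevalence fails in 0.2% of trials. Age and tumour size, recorded as numbers on CRF #1, would rarely separate if kept continuous.
- **Test.** An infinite estimate spoils the Wald test. A likelihood-ratio statistic remains defined, and Section 15.6 does not say which test is meant.
- **Event count.** Ten failures might be read as a cap. It is not: LR is undefined and follow-up runs past 3 years for many patients ("thus the expected median follow-up of the study population will be 3-4 years").
- **Weight.** Sections 1.3.2 and 4.2 ask for predictive covariates for cosmesis, not for recurrence. For local control they ask only for the 3-year rate.

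These limit the size of the point but do not remove it. None supplies a covariate list or a small-sample method, and none answers the low power.

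**Conclusion.** The point holds as a sparse-data and specification gap in a secondary association analysis. With roughly 4 to 12 failures, some effects, mainly of rare or multi-level factors, may have no finite estimate, and every significance test is weak. The firmest figures are those for multicatheter, the one covariate with a frequency set by the plan: about 8% at 10 expected failures and 30% at 5, taking the share at its 25% minimum. The 16–44% range for any of five covariates rests on assumed prevalences, independent covariates and no true effects. The failure counts over follow-up rest on a constant hazard, uniform accrual and local failures only. The low power needs only the failure count and the split: at 10 failures and 25:75, a true hazard ratio of 2 is detected about one time in six.

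Nothing here touches the primary toxicity rule or the Kaplan-Meier estimate of local control. It is a worthwhile improvement, not a defect in the trial's main conclusions.

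**What to change.** In Section 15.6, replace the parametric model and its significance criterion for LR failure with the following:

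- a short pre-specified covariate list, and a definition of LR that says whether regional failures count;
- one single-covariate Firth-penalised Cox model (or penalised Weibull model) per listed covariate;
- hazard ratios with profile-likelihood 95% intervals;
- an exploratory label, with no multivariable model and no significance claims at the expected event count.

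A cut-off that restored multivariable models or significance claims once 10 failures are reached would not help, because both the sparsity and the low power persist at 10. Penalisation keeps the estimates finite but does not create power; the wide intervals will show that.

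The cost is a few sentences of SAP text and standard software, with no extra patients or data. The downside is fewer significance statements about recurrence.

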## 15.7 Assumptions

See Sections 15.3.

## 15.8 Compliance and Missing Data

Compliance will be defined as patients who complete the course of radiotherapy in a time frame as described above. If a patient is unable to do so, they will be removed from the study. Data will be accumulated on a daily basis during treatment for each patient, and then in follow-up visits. If by chance there is missing data, it will be imputed based on the population as a whole.

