## **3. STUDY DESIGN**

This multiple site, prospective, non-randomized phase II study has been designed to determine the safety of delivering APBI with a brachytherapy applicator in a short course, 2-3 day fashion.

Data collected during this study will include baseline patient demographics, information related radiation therapy treatment delivery, toxicities, cosmetic outcomes and recurrence data. The patient's follow-up data will be collected during the patient's standard follow-up visits. All patients will be asked to return for clinic visits for a minimum of 2 years. The investigator will continue to review and collect data from the patient's medical record for disease status until the study is completed. This information will be collected to help in data analysis for the secondary objective and resolve any queries that may arise during data analysis and for publication.

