### **6.2 Exclusion Criteria**

- 6.2.1 Age  $< 45$  at diagnosis (regardless of histology)
- 6.2.2 Pregnant or breast-feeding
- 6.2.3 Active collagen-vascular disease (patients not on medication AND ESR $<20$  AND CPK in normal range are eligible for study)
- 6.2.4 Paget's disease of the breast
- 6.2.5 Prior history of DCIS or invasive breast cancer
- 6.2.6 Prior breast or thoracic RT for any condition
- 6.2.7 Multicentric carcinoma (DCIS or invasive)
- 6.2.8 Synchronous bilateral invasive or non-invasive breast cancer
- 6.2.9 Surgical margins that cannot be microscopically assessed or that are positive
- 6.2.10 Positive axillary node(s)
- 6.2.11 T stage of T2 with the tumor  $> 3$  cm in maximum diameter or a T stage  $\geq 3$
- 6.2.12 Estrogen receptor negative and progesterone receptor negative tumor

6.2.13 Any of the dosimetric treatment criteria as defined in Section 9.7 have not been met. Patients who become ineligible due to inability to meet dosimetric criteria should not receive treatment as defined in this protocol and will come off the study; any subsequent adjuvant radiation will be delivered at the discretion of the treating physician.

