#### **7.7.2 Patient Discontinuation**

7.7.2.1 A patient may be discontinued from the study at the discretion of the investigator if the patient's condition deteriorates or if the investigator decides that continuing in the study may be detrimental to the health or welfare of the patient.

7.7.2.2 Voluntary withdrawal from the study by the patient (note: voluntary withdrawal may occur at any time during the study and will not affect the patient's future medical treatment or benefits)

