Lumen 7:	 n/a  1  2  3  4  5  6  7  8  9  10  Other _____	_____ sec
Lumen 8:	 n/a  1  2  3  4  5  6  7  8  9  10  Other _____	_____ sec
Lumen 9:	 n/a  1  2  3  4  5  6  7  8  9  10  Other _____	_____ sec
Lumen 10:	 n/a  1  2  3  4  5  6  7  8  9  10  Other _____	_____ sec
19. Dose per Fraction:  7.5 Gy  Other _____	20. Number of Fractions:  3  Other _____	
21. RT Stop Date: _____ / _____ / _____ <small>M M D D Y Y</small>	22. Removal Date: _____ / _____ / _____ <small>M M D D Y Y</small>	

Treating Physician Signature: \_\_\_\_\_ Date: \_\_\_\_\_

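### Section 15.8 removes every patient who does not finish radiotherapy on time, whatever the reason, and the plan does not say whether she is still counted or followed for the primary toxicity endpoint

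*Combined protocol and SAP*

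**What the plan says.** Section 15.8, in the statistical chapter, defines compliance: "Compliance will be defined as patients who complete the course of radiotherapy in a time frame as described above". Sections 7.4 and 9.5 give the time frame as three fractions over 2-3 days. For a patient who does not manage this, 15.8 continues: "If a patient is unable to do so, they will be removed from the study". No reason for non-completion is exempt. On gaps in the data, the same section adds: "If by chance there is missing data, it will be imputed based on the population as a whole".

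On follow-up, Section 3 says: "All patients will be asked to return for clinic visits for a minimum of 2 years". Section 7.7.2 gives two routes out of the study, voluntary withdrawal and investigator decision ("A patient may be discontinued from the study at the discretion of the investigator").

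On the decision, Section 15.3 says: "In a cohort of 200 patients, there should be 11 or fewer serious toxicities to exclude a rate of 10" per cent. Sections 1.4.1 and 5.1.1 repeat this. Sections 11 and 15.3 restrict the events that count to those above CTCAE grade 2 with probable or definite attribution. None of these sections defines the 200 as registered, treated or compliant patients.

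**The concern.** The trial has one arm, and its primary conclusion rests on a count of treatment-attributed toxicities. If a toxicity interrupts the course, the patient becomes a non-completer because of the outcome being measured, and 15.8 then takes her out of the study. Section 11 assesses the endpoint at follow-up visits, which a removed patient may no longer have. Two things could therefore be lost: the event that stopped treatment, and any later toxicity from the fractions she did receive. If her 2-year outcome is instead treated as missing, imputation from the whole study population gives her an average risk, which is too low for someone removed because of toxicity.

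Removing patients without an event shrinks the denominator and makes the safety limit harder to meet. Without a defined analysis population, two analysts could follow the text and reach different conclusions from the same patients.

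**Working it through.** **Inputs.** N = 200, limit of 11 events, unacceptable rate 10%, assumed conventional rate 3% (all Section 15.3). The documents give no rate of non-completion, so the shares of lost events in step 4 are assumptions.

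**1. The plan's own figure.** Section 15.3 names no interval method. The exact (Clopper-Pearson) two-sided 95% upper limit U solves P(Bin(n, U) ≤ x) = 0.025.

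| Count | Exact | Wilson | Agresti-Coull |
|---|---|---|---|
| 11/200 | 9.63% | 9.58% | 9.68% |
| 12/200 | 10.25% | 10.19% | 10.29% |

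All three methods give a limit of 11, so the stated figure is reproduced. A one-sided exact limit would allow 12 and a Wald limit 13.

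**2. One patient with an event is removed.** Suppose 12 of 200 treated patients have a serious toxicity and one of them is removed as a non-completer.
- All counted: 12/200, exact limit 10.25%, unsafe.
- Her data dropped: 11/199, exact limit 9.68%, safe (Wilson 9.63%, Agresti-Coull 9.73%).

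One lost event changes the decision only if the full count is exactly 12. From Bin(200, p), P(X = 12) is 1.1% at p = 0.03 and 1.5% at p = 0.10.

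**3. Event-free patients are removed.** Suppose the full count is 11 and eight non-completers without an event are removed (200 − 8 = 192).
- All counted: 11/200, exact limit 9.63%, safe.
- Eight removed: 11/192, exact limit 10.02%, unsafe.

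This is the opposite direction. It depends slightly on the method: the Wilson limit at 11/192, from (p + z²/2n + z√(p(1−p)/n + z²/4n²))/(1 + z²/n) with p = 11/192 and z = 1.96, is 9.97%, still just safe.

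**4. A share s of serious events is lost.** Each event is lost independently with probability s, and the patient leaves the denominator without replacement. The number lost is R ~ Bin(200, ps). Given R, the counted events follow Bin(200 − R, p(1 − s)/(1 − ps)). Safety is declared if the exact limit for 200 − R patients does not exceed 10%. Summing over R:

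| True rate p | s = 0 | s = 2% | s = 5% |
|---|---|---|---|
| 10%: chance of declaring safe | 1.68% | 2.08% | 2.86% |
| 3%: chance of declaring safe | 98.16% | 98.40% | 98.72% |
| 10%: expected lost events, 200ps | 0 | 0.4 | 1.0 |
| 3%: expected lost events, 200ps | 0 | 0.12 | 0.30 |

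This model removes only patients with events, so it shows one side of the bias and not the net effect.

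**5. Does any section close the gap?** Section 7.6 monitors adverse events continuously, Section 15.8 collects data daily during treatment, Section 7.7 requires an exit form for every participant, and Appendix 4 requires serious adverse events arising in the study to be reported. These make it likely that an event during treatment is recorded. None says that a removed patient's event enters the primary count, that she stays in the denominator, or that she is seen at 2 years.

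**The case against.** The strongest defence is that the plan leans toward counting. Section 15.8 speaks of removal from the study and not of deleting data. The counting rule in Sections 11 and 15.3 tests grade and attribution only, with no exception for removed patients. Section 7.1 places a patient on study at registration. This stands in part. A reader might infer that the plan discards toxicity already recorded, or that imputation overwrites it. The documents support neither: they are silent on the first, and the imputation sentence covers only missing data. But the removal sentence stands in the statistical chapter under compliance and missing data, where an analyst could well take it as an analysis rule. Even on the mild reading it ends follow-up.

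A reader might also infer a flat contradiction with Sections 3 and 7.7.2. That is too strong. The request in Section 3 is general, and other rules already qualify it: patients who fail the dosimetric criteria come off the study (6.2.13), and 7.7.2 allows discontinuation, including when a patient's condition deteriorates. Section 7.7.2 does not claim to be complete. What remains is that the passages do not say which governs a patient who was treated but did not finish.

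The mechanism is also narrow. A loss needs a toxicity above grade 2, with probable or definite attribution, that interrupts a 2-3 day course. Section 2.4 reports 45 + 30 = 75 patients on a different 2-day schedule with no grade 3 toxicity. This stands, and it limits the expected size.

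Finally, it is tempting to say that the rule biases toward safety. That holds only for removals caused by toxicity; step 3 shows the reverse for event-free removals.

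**Conclusion.** The concern holds as a gap in the analysis population combined with a removal rule that can depend on the outcome. The plan should be changed, but the flaw is not fatal. The stated limit of 11 in 200 is correct under the three two-sided methods above. The net direction of the bias is unknown, because the documents do not say how many patients will fail to complete, or why.

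The expected effect is probably small. If 2% to 5% of serious events were lost (an assumption), the chance of declaring a true 10% rate safe would rise from 1.68% to between 2.08% and 2.86%. At a true 3% rate the chance of declaring safety would change by 0.2 to 0.6 percentage points. The reason to act is that at the limit the conclusion turns on an undefined choice. One lost event turns unsafe into safe, and eight event-free removals turn safe into unsafe under the exact method.

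**What to change.** Replace the removal sentence in Section 15.8 with wording to this effect: every patient who received at least one protocol fraction is in the primary toxicity analysis, numerator and denominator, and is followed for 2 years; non-completion is recorded as a protocol deviation with its reason; toxicity recorded before any withdrawal of consent is counted; withdrawal ends only further data collection. State in Sections 1.4.1, 5.1.1 and 15.3 that the 200 are these treated patients. Report completers only as a sensitivity analysis, and flag patients with a partial course or later radiation outside the protocol.

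The cost is wording, routine follow-up of probably few patients, and small additions to the forms. CRF #2 already records the start and stop dates and the "Number of Fractions", but has no field for the reason for non-completion. Later radiation could be entered only under the open category of the adjuvant therapy item on CRF #3.

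There is a statistical price. A partial course may dilute late toxicity. Later radiation may add toxicity that is not due to the study schedule; Section 6.2.13 foresees such treatment for patients who fail the dosimetric criteria ("any subsequent adjuvant radiation will be delivered at the discretion of the treating physician"). The attribution rule and the sensitivity analysis show how far this matters. Patients who fail those criteria before any fraction are a separate case and stay outside this analysis set. The change concerns only who is followed and counted, and alters no treatment rule.

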#### **7.7.1 Patient Completion**

A patient is considered to have completed the study if the follow-up examinations were completed through year 2.

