#### **7.7.3 Patient Lost to Follow-Up**

A patient may be lost to follow-up for non-treatment related reasons. Reasons for loss to follow-up include, but are not limited to:

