## 15.5 Outcome Measures

The primary endpoint will be measured by the data collected for toxicity and cosmesis as dichotomous variables. Time to local failure will be recorded for secondary endpoint analysis.

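### The blanket imputation rule in section 15.8 does not exempt the 2-year serious-toxicity endpoint; applied there, it narrows the upper limit and can turn a borderline unsafe result into a safe one

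*Combined protocol and SAP*

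**What the plan says.** Section 15.8 (Compliance and Missing Data) first describes data collection: "Data will be accumulated on a daily basis during treatment for each patient, and then in follow-up visits". The next sentence is the missing-data rule: "If by chance there is missing data, it will be imputed based on the population as a whole". It gives no method, rounding rule or list of variables. Section 15.6 has no missing-data rule for toxicity.

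The primary decision is in section 15.3 and is repeated in 1.4.1 and 5.1.1. The treatment counts as unsafe unless the 95% interval excludes a 2-year serious-toxicity rate above 10%. For 200 patients, "if we observe up to 11 serious toxicities, the upper 95% confidence limit will not exceed 0.10". Section 15.3 adds: "The relative threshold toxicity rates for different sample sizes has been generated and is available for review from the PI". Those thresholds are not printed. Section 15.5 makes the endpoint binary: "The primary endpoint will be measured by the data collected for toxicity and cosmesis as dichotomous variables".

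Incomplete follow-up is foreseen. Under 7.7.1, "A patient is considered to have completed the study if the follow-up examinations were completed through year 2"; under 7.7.3, "A patient may be lost to follow-up for non-treatment related reasons". No section says how a patient without a 2-year status enters the toxicity decision.

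**The concern.** The trial has one pass/fail safety decision, and it rests on the upper limit of a binomial interval. Single imputation from the whole population keeps the estimated rate about where it was but raises the denominator to 200. The interval is then computed as if 200 outcomes had been seen, so its upper limit is too low.

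Because 15.3 points one way and the general rule in 15.8 another, the choice between observed cases and one of several fills could be made after the data are seen. Near the limit these give different verdicts on the same data. Two-year cosmesis has the same gap.

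**Working it through.** **Inputs.** From 15.3: N = 200, limit 11 events, unacceptable rate 10%, assumed rate 3%, 95% interval with no method named. Assumed, because the documents give no missingness rate: 160 to 199 patients with a known 2-year status, missingness unrelated to toxicity, and a two-sided exact (Clopper-Pearson) interval.

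**Formula.** For x events in n patients, the upper limit U(x, n) is the 0.975 quantile of Beta(x+1, n−x).

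**Step 1: the plan's own figure.** U(11, 200) = 9.63% and U(12, 200) = 10.25%. The limit of 11 reproduces, as it does with Wilson (9.58%, 10.19%) and Agresti-Coull (9.68%, 10.29%). The chance of 11 or fewer events in 200 is 98.2% at a true 3% and 1.7% at a true 10%.

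**Step 2: observed cases only.** The largest passing counts are:

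| Allowed events | Clopper-Pearson, n | Agresti-Coull, n |
|---|---|---|
| 11 | 193–200 | 194–200 |
| 10 | 180–192 | 181–193 |
| 9 | 167–179 | 169–180 |
| 8 | 154–166 | 156–168 |

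**Step 3: filling back to 200.** Filling the 200−n missing patients at the observed rate gives a total of x + (200−n)·x/n = 200x/n. For 10 events in 175:
- observed: U(10, 175) = 10.26%, unsafe;
- filled total: 10 × 200/175 = 11.43;
- rounded to 11: U(11, 200) = 9.63%, safe;
- unrounded in the same formula: U(11.43, 200) = 9.89%, safe.

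**Step 4: where the verdict changes, n = 160 to 199.** Rounded fill changes it at 9/160–166, 10/174–179 and 11/192. That is 7 + 6 + 1 = 14 of the 40 values of n, each at a single count. The exact limit at the unrounded total adds 10/173 and 11/190–191. Every one of these changes is from unsafe to safe. A random draw for each missing patient can go either way: 11/190 (observed limit 10.12%, unsafe) passes with probability 0.55, and 10/180 (9.98%, safe) passes with probability 0.69.

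**Step 5: chance of a safe verdict at a true 10% rate.** Observed: P(X ≤ allowed count at n). Rounded: P(X ≤ largest x for which 200x/n rounds to 11 or less). Random draw: Binomial(n, 0.10) combined with Binomial(200−n, x/n), total at most 11.

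| n observed | Observed cases | Rounded fill | One random draw |
|---|---|---|---|
| 180 | 2.45% | 2.45% | 2.63% |
| 170 | 2.09% | 2.09% | 3.20% |
| 160 | 1.74% | 3.59% | 3.85% |
| maximum over 160–199 | 2.46% | 3.59% | 3.85% |

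At n = 160, for example, 9 events fill to 9 × 200/160 = 11.25, which rounds to 11 and passes; on observed cases only 8 are allowed.

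**Step 6: how often it matters.** Over n = 160 to 199, the chance of landing on a count where rounded fill changes the verdict averages 1.0% at a true 3% rate (maximum 3.5%) and 4.3% at an illustrative 5% (maximum 13%). At 5% with n = 175, the chance of passing is 62.1% on observed cases and 73.9% with rounded fill.

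**The case against.** The best defence is that 15.3 already settles the matter. It speaks of events observed, it mentions thresholds for other sample sizes (needed only if the denominator may differ from 200), and 15.5 refers to data collected. A specific rule would normally override one general sentence. This stands as the likelier intention, so a reader should not infer that the plan prescribes imputed toxicity events. It does not remove the gap: 15.8 is stated as a rule, follows directly on follow-up data and exempts nothing, and the unprinted thresholds are not described as replacing it.

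The second defence is size. That also stands: verdict changes need a count at one particular value, and there are none under rounded fill at n = 180 or 170.

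Two stronger readings are tempting and not supported:
- A reader might compare the unrounded 11.43 with 11 and conclude that filling also makes safe results unsafe. The plan's criterion is the upper limit, and 11 is only its value at n = 200; 11.43 in 200 has a limit of 9.89% and passes.
- A reader might fill every missing patient as event-free, which takes the error at n = 160 to 11.4%. Nothing in 15.8 says this, and it is the least natural reading of a fill from the whole population.

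**Conclusion.** The concern holds in a limited form: a stated rule, if applied to the primary endpoint, understates uncertainty and can pass a result that the observed data would fail. The limit of 11 in 200 is correct and is not in question.

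The rise in the chance of wrongly declaring safety is small: 3.59% or 3.85% at most, against 2.46%. These figures rest on assumed missingness of up to 20%, unrelated to toxicity, and on the exact interval; Agresti-Coull moves the cut-points by one or two patients. Informative loss would bias an observed-case analysis as well and is not claimed here.

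Local control is unaffected, because Kaplan-Meier is specified. Nor should a reader infer that toxicities before loss go uncounted, since 7.6 requires continuous monitoring. For cosmesis the gap is one of wording only; no effect was calculated. Weight: minor to should-fix.

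**What to change.** In 15.8, state that the serious-toxicity endpoint and 2-year cosmesis are not imputed. In 15.3 and 15.6, base the decision on observed data in one of two ways:

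- Preferred: the 2-year cumulative incidence of first serious toxicity, censored at the last toxicity evaluation, with its upper two-sided 95% limit compared with 10%.
- Alternative: evaluable patients, with evaluable defined, the interval method named and the allowed counts printed for the actual n (the table above gives them for two methods). The reference list contains a paper on the Agresti-Coull interval, but no section ties it to this decision, so the choice must be stated.

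Show a worst-case fill, with every missing patient an event, only as a labelled sensitivity analysis.

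The cost is wording; no new data are needed. The allowed count falls slightly when follow-up is incomplete. With exact limits, the chance of passing at a true 3% rate is 98.2/97.1/97.9/96.7/94.7% at n = 200/190/180/170/160.

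The alternative has a further cost that should be disclosed. Counting toxicities recorded before loss while dropping event-free lost patients is conservative. If half of the 2-year risk in lost patients is recorded before loss (assumed), then with 20/30/40 of 200 lost the chance of passing is 97.1/94.6/90.6% at a true 3% and about 65/55/45% at a true 5%, where full follow-up would give 70.0%. The censored estimate avoids this, which is why it is preferred.
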